6.2.3 Follow-up period and trial completion

End-of-Treatment Visit

Patients who prematurely discontinue the trial at any time after Day 1 (but do not withdraw their consent) will be required to have all of the evaluations for the Week 50 Visit as soon after trial discontinuation as possible.

Every effort should be made for all patients who complete the total 50-week treatment period, or who discontinue the trial early, to return for an SFU Visit at Week 58 or 10 weeks after the last treatment administration.

Unscheduled visit assessments

Patients may attend the trial site for unscheduled visits at any time for additional safety monitoring at the discretion of the Investigator.

Page 56 of 105

Proprietary confidential information © 2019 Boehringer Ingelheim International GmbH or one or more of its affiliated companies

7. STATISTICAL METHODS AND DETERMINATION OF SAMPLE SIZE

7.1 STATISTICAL DESIGN - MODEL

This is a randomized, double-blind, parallel-arm, multiple-dose, active comparator, multi-center, multi-national trial.

Trial objectives are as stated in Section 2.1.1.

7.2 NULL AND ALTERNATIVE HYPOTHESES

For the primary endpoint analysis the BE margins 80% - 125% on the ratio scale will be applied.

The two endpoints are considered coprimary (i.e., the trial is considered positive if the results for both endpoints are simultaneously positive), therefore no multiplicity-adjustment with respect to the alpha level will be performed.

The tests for PK similarity will be performed with respect to switching versus continuous Humira.

The hypotheses for the primary endpoint analysis can be written as follows:

- H_{01} : Ratio of the means of $AUC_{\tau, 30-32}$ (switching arm versus continuous Humira® arm) is less than 80% or more than 125%
- H_{11} : Ratio of the means of $AUC_{\tau, 30-32}$ (switching arm versus continuous Humira® arm) is within [80%, 125%]

and

- H_{02} : Ratio of the means of $C_{max, 30-32}$ (switching arm versus continuous Humira[®] arm) is less than 80% or more than 125%
- H_{12} : Ratio of the means of $C_{max, 30-32}$ (switching arm versus continuous Humira® arm) is within [80%, 125%]

A (one-sided) significance level 4.9% was chosen to ensure overall type I error control at 5%, in light of the adapted analysis strategy (details are described in the TSAP).

7.3 PLANNED ANALYSES

Pharmacokinetic parameters of a patient will be included in the statistical analyses of PK endpoints if they are not flagged for exclusion due to a protocol violation relevant to the evaluation of PK. Whether a protocol violation is considered relevant will be decided no later than in the Data Review Meeting (DRM) prior to the data snapshot. Exclusion of a patient's data will be documented in the CTR.

Relevant protocol violations within the time period critical for primary endpoint evaluation (i.e., from Visit 2 to 18) may be:

Page 57 of 105

Proprietary confidential information © 2019 Boehringer Ingelheim International GmbH or one or more of its affiliated companies

- Incorrect trial medication taken, i.e., the patient received at least one dose of trial medication the patient was not assigned to.
- Incorrect or incomplete dose of trial medication taken.
- Missed doses of trial medication.
- Use of restricted medications with suspected impact on PK.
- Missed plasma samples during the dosing interval from Week 12 to Week 14 or from Week 30 to Week 32:
 - o at two consecutive timepoints during Visits 8a-d and 17a-d
 - o before dosing at Week 12, 14, 30 or 32.

Further criteria that may lead to exclusion of subjects or individual plasma concentrations from the calculation of PK parameters or exclusion of PK parameters from statistical analyses may be specified in the TSAP and in the minutes of the Data Review Meeting.

The PKS includes all patients in the Treated Set (TS, see below) who provide at least one primary PK parameter that was not excluded according to the description above.

All efficacy analyses will be based on the Per Protocol Set (PPS).

The PPS consists of all patients

- who were randomized to double-blinded treatment
- who received at least one dose of double-blinded trial medication, and
- who have all efficacy measures relevant for at least one secondary efficacy endpoint, measured prior to randomization (last non-missing value prior to randomization) and at least once post-randomization.
- who have followed the CTP in all essential criteria: violations relevant for efficacy will be excluded from the PPS. A protocol violation will be considered important if it can be expected to have a distorting influence on the assessment of the secondary efficacy endpoint. Important protocol violations may include: Incorrect trial medication taken, violation of treatment compliance, violation of inclusion/exclusion criteria. Protocol violations will be assessed on a case-by-case basis. Further details on the definition of the different analysis sets will be provided in the TSAP.

All patients treated with at least one dose of trial medication administered in the randomized phase will be included in the safety evaluation (TS).

All patients treated with at least one dose of Humira® during the run-in period will be included in the Run-in Treated Set (RTS).

The primary, secondary and further analysis results will be presented based on the double-blind randomization (continuous Humira® arm and switching arm).

7.3.1 Primary endpoint analyses

The analyses will be performed on the PKS and done 'as treated'.

The PK similarity of the two treatments (switching arm versus continuous Humira[®] arm) will be tested for the primary parameters $AUC_{\tau, 30-32}$ and $C_{max, 30-32}$ (see Section 2.1.2 for details).

Page 58 of 105

Proprietary confidential information © 2019 Boehringer Ingelheim International GmbH or one or more of its affiliated companies

The ratios of the means including their two-sided 90.2% CIs will be calculated. The confidence interval will be calculated according to Fiellers theorem [R12-1809]. As stated in [R12-1809, chapter 10.2.1], equivalence will be concluded if Fieller's 90.2% confidence interval for the ratio of means is included in the equivalence range 80.00% - 125.00% and

$$\frac{|\overline{Y}_R|}{\hat{\sigma}\sqrt{\frac{1}{n_R}}} > t_{1-\alpha,n_T+n_R-5}$$

which is equivalent to rejecting both null hypotheses. Thereby \bar{Y}_R refers to the LSMean of the reference treatment, $\hat{\sigma}$ is the residual standard deviation from the ANCOVA model (M1) below, n_T and n_R are the final sample sizes in the test and reference arm, respectively, and $\alpha = 4.9\%$.

The statistical model used for the analysis of $AUC_{\tau, 30-32}$ and $C_{max, 30-32}$ will be an analysis of covariance (ANCOVA) model on the original scale. This model will include effects accounting for:

- Treatment (switching arm versus continuously Humira® arm)
- Logarithm of rPASI, where rPASI is the ratio of PASI at Week 14 and PASI at Week 1 (continuous value)
- Weight at Week 14 (continuous value)
- Stage, where stage represents the two parts of the study prior to and after the blinded sample size reassessment (categorical, 1 or 2)
- AUC_{τ . 12-14} or C_{max. 12-14} (continuous value)

as a source of variation. As the measurements at Week 14 will be prior to randomization and all patients will have received the same treatment with the reference treatment only, the covariates listed above are all considered adequate baseline values.

All effects will be considered as fixed. The model is described by the following equation: (M1) response (AUC $_{\tau}$ or C $_{max}$) = overall mean + treatment effect + log(rPASI) + weight at Week 14 + stage + AUC $_{\tau}$, 12-14 or C $_{max}$, 12-14 + random error.

where the random errors are assumed to be independent and normally distributed with zero mean and variance σ_k^2 where k is either test or reference treatment.

Prior to analysis, the data will be log-transformed (see M1). In other words, the dependent variable of the primary endpoint analysis model is the primary endpoint, as stated in the M1 formula. The analysis will then be adjusted for the covariates as stated in M1. The model will be implemented with the SAS® procedure PROC MIXED in conjunction with the LSMEANS statement. The LSMEANS statement is used to estimate the treatment. LSMeans of the switching and non-switching arm which will be used to construct the point estimate for the ratio of means. The 90.2% CI will be derived based on Fieller's theorem.

All patients that finished Week 32 Visit at or before the cut-off date will be allocated to stage 1. All other patients (i.e., all patients that at cut-off date do not have a finished Week 32 Visit) will be allocated to stage 2.

Page 59 of 105

Proprietary confidential information © 2019 Boehringer Ingelheim International GmbH or one or more of its affiliated companies

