mode of administration:	s.c. injection							
Duration of treatment:	Patients will be treated with trial medication for 48 weeks.							

16011431-03 Clinical Trial Protocol Page 4 of 105

Proprietary confidential information © 2019 Boehringer Ingelheim International GmbH or one or more of its affiliated companies

Company name	Boehringer Ingelheim
Finished product name	NA NA
Active ingredient name:	BI 695501
Protocol date	Revision date 25 Jul 2019
Trial number	1297.9
Endpoints	The following will be the endpoints of the trial:
	Primary endpoints: Pharmacokinetics • AUC _{τ, 30-32} (Area under the adalimumab plasma concentration-time curve [AUC] over the dosing interval of Week 30-32) • C _{max, 30-32} (Maximum observed adalimumab plasma concentration during the dosing interval Week 30-32)
	Secondary endpoints:
	 Pharmacokinetics C_{min, 30-32} (Minimum observed adalimumab plasma concentration during the dosing interval Week 30-32) t_{max, 30-32} (Time to maximum observed adalimumab plasma concentration during the dosing interval Week 30-32) Efficacy Proportion of patients with a 75% reduction in PASI (PASI75) response at Week 32 Proportion of patients with an sPGA ≤ 1 (clear or almost clear) at Week 32 Safety Proportion of patients with drug-related adverse events (AEs) during the treatment phase and the safety follow-up period
	 Immunogenicity Proportion of patients with anti-drug antibodies (ADAs) and ADA titer at Week 32, Proportion of patients with neutralizing ADAs (nAbs) frequency and
Safety criteria:	titer at Week 32 Physical examination, vital signs (blood pressure, pulse rate, and body temperature), 12-lead electrocardiogram (ECG), laboratory tests, continuous AE monitoring and local tolerability.
Statistical methods:	The assessment of PK similarity will be based upon two-sided 90.2% confidence intervals (CIs) for the ratios of the means (test/reference, where the test treatment corresponds to the switching arm and the reference to the Humira only arm) for the primary endpoints using an acceptance range of 80.00% to 125.00%. This method is equivalent to the two one-sided t-tests procedure, each at the 4.9 significance level The statistical model will be an analysis of covariance (ANCOVA) on the original scale including effects for "treatment", "log(rPASI)", "weight", and "AUC $_{\tau, 12-14}$ " or "C $_{max, 12-14}$ ", where rPASI=ratio of PASI at Week 14 and PASI at Week 1.

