3. DESCRIPTION OF DESIGN AND TRIAL POPULATION

3.1 OVERALL TRIAL DESIGN AND PLAN

This is a 58-week, multiple-dose, active comparator trial with a single-arm run-in period of 14 weeks duration for all entered patients, followed by a randomized, double-blind, two-arm period of 34 weeks. The total treatment period will be 48 weeks followed by 10 weeks of safety follow-up.

All entered patients will have a planned run-in period of 14 weeks during which they will be treated with US-licensed Humira[®] (last dose at Week 12/Visit 8) (see Section 4.1 for dosage). At the beginning of Week 14 (Visit 9), patients achieving at least a PASI50 response will be randomized in a 1:1 ratio to either continue receiving US-licensed Humira[®] (continuous US-licensed Humira[®] arm) until Week 48 or receive BI 695501/US-licensed Humira[®]/BI 695501 alternately for three periods (switching arm) in a blinded fashion (BI 695501 at Week 14/Visit 9 and Week 16/Visit 10, US-licensed Humira at Week 18/Visit 11 and Week 20/Visit 12, and BI 695501 every other week from Week 22/Visit 13 to Week 48/Visit 26). At Week 14, the randomization will be stratified by the level of their Week 14 PASI response (≥ PASI50 to < PASI75 and ≥ PASI75). All patients will continue to receive 40 mg US-licensed Humira[®] or BI 695501 every other week until Week 48.

[figure not shown]
Those patients not achieving at least PASI50 at Week 14 will be discontinued from any further treatment in the trial, but will undergo the End-of-Treatment (EoT) and Safety Follow-up (SFU) for safety.

[figure not shown]
Patients will undergo intensive PK sampling between Weeks 12-14 (Visit 8, Visits 8a-d, and Visit 9), and Weeks 30-32 (Visit 17, Visits 17a-d, and Visit 18) to assess PK similarity between the two arms.

The co-primary PK endpoints of the trial are $AUC_{\tau, 30-32}$ and $C_{max, 30-32}$ (see Section 2.1.2). After approximately 86 patients have had the Week 32 endpoint assessment and are PK evaluable, a statistician will perform a blinded evaluation of the variability to assess whether the initially planned sample size will be increased or not.

Figure 3.1: 1 summarizes the trial design.

Page 25 of 105

Note: Trial medications are administered at the beginning of the specified week.

Figure 3.1: 1 Trial Design

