3.3.2 Inclusion criteria

- 1. Males and females aged ≥ 18 to < 80 years at screening who have a diagnosis of moderate-to-severe chronic plaque psoriasis (with or without psoriatic arthritis) for at least 6 months before the first administration of trial drug (a self-reported diagnosis confirmed by the Investigator is acceptable), and which has been stable per Investigator opinion for the last 2 months with no changes in morphology or significant flares at both screening and baseline:
 - a. involved body surface area (BSA) $\geq 10\%$ and
 - b. PASI score ≥ 12 and
 - c. sPGA score of ≥ 3 .
- 2. Participants of reproductive potential (childbearing potential²) must be willing and able to use highly effective methods of birth control per International Council for Harmonisation (ICH) M3 (R2) that result in a low failure rate of less than 1% per year when used consistently and correctly during the trial and for 6 months following completion or discontinuation from the trial medication. A list of contraception methods meeting these criteria is provided in the Section 4.2.2.3 and patient information.
- 3. Signed and dated written informed consent in accordance with Good Clinical Practice (GCP) and local legislation prior to admission to the trial.
- 4. Patients who are candidates for systemic therapy or phototherapy according to Investigator judgement.

² A woman is considered of childbearing potential (WOCBP), i.e. fertile, following menarche and until becoming postmenopausal unless permanently sterile.

Permanent sterilisation methods include hysterectomy, bilateral salpingectomy and bilateral oophorectomy. Tubal ligation is NOT a method of permanent sterilisation.

A postmenopausal state is defined as no menses for 12 months without an alternative medical cause.

Page 27 of 105

Proprietary confidential information © 2019 Boehringer Ingelheim International GmbH or one or more of its affiliated companies

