5.1.1 PASI

The PASI is an established measure of clinical efficacy for psoriasis medications (R96-3541).

The PASI is a tool which provides a numeric scoring for patients' overall psoriasis disease state, ranging from 0 to 72. It is a linear combination of percent of surface area of skin that is affected and the severity of erythema, induration, and desquamation over four body regions.

The endpoints used are based on the percent reduction from baseline, generally summarized as a dichotomous outcome based on achieving over an X% reduction (or $PASI_X$), where X is 50, 75, 90, and 100.

To calculate the PASI, the 4 main body areas are assessed: **head (h), trunk (t), upper extremities (u) and lower extremities (l)**. These correspond to 10%, 30%, 20%, and 40% of the total body area, respectively.

The area of psoriatic involvement of these four areas (Ah, At, Au, and Al) is given a numerical value: 0 = no involvement, 1 = < 10%, 2 = 10% to < 30%, 3 = 30% to < 50%, 4 = 50% to < 70%, 5 = 70% to < 90%, and 6 = 90% to 100% involvement (Table 10.2: 2).

The signs of severity, erythema (E), induration (I) and desquamation (D) of lesions are assessed using a numeric scale 0-4 where 0 is a complete lack of cutaneous involvement and 4 is the severest possible involvement; scores are made independently for each of the areas, h, t, u, and l and represent a composite score for each area. An illustration of judging erythema follows: 0 = no erythema, 1 = slight erythema, 2 = moderate erythema, 3 = severe erythema, and 4 = very severe erythema.

The PASI score is calculated according to the following formula: PASI = 0.1(Eh+Ih+Dh)Ah + 0.3(Et+It+Dt)At + 0.2(Eu+Iu+Du)Au + 0.4(El+Il+Dl)Al (Appendix 10.2, Table 10.2: 4)

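### The primary ANCOVA adjusts for log(rPASI), which is undefined for a patient with PASI 0 at Week 14, so M1 as written drops any complete responder despite valid PK data

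*Protocol*

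**What the plan says.** Section 7.3.1 lists, among the effects in M1, "Logarithm of rPASI, where rPASI is the ratio of PASI at Week 14 and PASI at Week 1 (continuous value"). The Synopsis (Statistical methods) has the same term, "where rPASI=ratio of PASI at Week 14 and PASI at Week 1". Section 7.3.1 then commits to that form: "The analysis will then be adjusted for the covariates as stated in M1". It also names the population: "The analyses will be performed on the PKS". Section 7.3 admits to the PKS any treated patient with at least one primary PK parameter that has not been excluded, and sets no condition on PASI.

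On the values PASI can take, Section 5.1.1 describes a score of "overall psoriasis disease state, ranging from 0 to 72" and lists percentage-reduction response levels "where X is 50, 75, 90, and 100". Inclusion criterion 1 (Section 3.3.2) requires "PASI score ≥ 12 and" at screening and baseline. On who is randomised, Section 3.1 says "patients achieving at least a PASI50 response will be randomized in a 1:1 ratio".

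Section 7.3.2.1 analyses Cmin in the same way as the primary endpoints. Section 7.4.1 takes the blinded variance from the same model, leaving out only treatment and stage.

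**The concern.** The protocol fixes an exact functional form that does not exist for some patients it randomises. A patient whose skin is clear at Week 14 is eligible, is treated, can supply complete Week 30-32 PK data and belongs to the PKS. Such a patient has no value for log(rPASI), because the numerator of the ratio is zero. A mixed-model procedure does not use a row with a missing covariate, so the patient leaves the primary model silently.

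This is not a missing-data problem, since the PASI score was observed. Valid primary PK data are lost only because of how a baseline covariate is transformed. The result would be less precise and would describe the PKS without its complete responders. The Cmin analysis and the blinded variance estimate inherit the same gap.

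**Working it through.** **The plan's own counts.** From the Synopsis: 240 entered, about 80% reaching PASI50, 10%-15% not PK evaluable.
- 240 × 0.80 = 192 randomised, or 96 per arm.
- 96 × (1 − 0.10) = 86.4 per arm. This reproduces the stated 86 at the lower end of the loss range.
- The two-arm total is 172.8. Section 7.4.1 sets the minimum at 170, which is used below.

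**Where the covariate fails.**
- Denominator: PASI at Week 1 ≥ 12, so it is never zero.
- Numerator: the smallest non-zero PASI under the formula in Section 5.1.1 is 0.1 × 1 × 1 = 0.1. This gives log(0.1/12) = −4.79 at the lowest eligible baseline and log(0.1/72) = −6.58 at the highest. Both are finite.
- At PASI 0, log(0/PASI1) is undefined for every baseline. Only exact zeros fail.
- In a simulated data set of 172 patients with 17 Week 14 scores set to zero, a least-squares fit with M1's terms used 155 rows.

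**Size.** Let z be the share of patients with PASI 0 at Week 14. The protocol gives no value, so z is assumed. With the same residual variance and similar loss in both arms, the interval widens by 1/√(1 − z) − 1.

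| z (assumed) | Lost from 170 | Left in M1 | Widening | Widening with t quantiles, n − 6 df |
|---|---|---|---|---|
| 5% | 8.5 | 161.5 | 2.6% | 2.6% |
| 10% | 17 | 153 | 5.4% | 5.5% |
| 20% | 34 | 136 | 11.8% | 12.0% |

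The chance that at least one of 170 patients is affected is 1 − (1 − z)^170. This is 82% at z = 1% and 97% at z = 2%.

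**Why the repair needs a stated constant.** With log((PASI14 + c)/(PASI1 + c)) and a baseline PASI of 20:

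| Week 14 PASI | c = 0.1 | c = 1 |
|---|---|---|
| 0 | log(0.1/20.1) = −5.30 | log(1/21) = −3.04 |
| 1 | log(1.1/20.1) = −2.91 | log(2/21) = −2.35 |
| Step from 1 to 0 | log(1.1/0.1) = 2.40 | log(2/1) = 0.69 |

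The constant decides how far cleared patients sit from the rest on the covariate axis, and hence their leverage.

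**The case against.** The strongest reply is that a boundary rule for one covariate is a derivation detail that belongs in the TSAP. That document was not available here, and the protocol defers to it often. A TSAP rule for PASI 0 could complete Section 7.3.1 without contradicting it. The possibility stands, but it does not remove the point. The protocol does not leave the covariate open: it states a form and commits to it, and that form fails on observed data from eligible patients. The deferrals in Sections 7.3, 7.4.1 and 7.6.3 concern exclusions and analysis sets, details of the re-assessment, and missing data. None covers an observed score of zero.

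A second reply is that Section 7.4.1 counts as PK evaluable only PKS members whose needed covariates are all present. The 170 may therefore already exclude cleared patients, and planning and analysis would then be consistent. This limits the claim. The section does not say whether an observed PASI 0 counts as present, so no shortfall against the planned 170 and no extra recruitment is asserted. The widening figures compare the analysis only with one that keeps these patients.

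Third, the rates are assumed and no imbalance between arms is expected. Both are true, and both bound the finding.

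**Conclusion.** The point holds. As written, M1 cannot be fitted on the whole PKS if any member had PASI 0 at Week 14. Cleared patients with valid primary PK parameters drop out of the primary and Cmin analyses, and the same term is in the blinded variance model.

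The effect is on precision and on the population described. Among 170 patients otherwise available to M1, it runs from nothing (no cleared patients) to an interval about 3%, 5% or 12% wider at assumed clearance rates of 5%, 10% or 20%. Week 14 PASI precedes randomisation, so the loss should not favour either arm. The point should be fixed before unblinding, but it does not invalidate the design. Confidence in its practical size is only moderate, because the protocol gives no clearance rate and the TSAP may contain a rule.

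**What to change.** While the study is blinded, replace the term with one that is defined at zero. One option is log((PASI14 + c)/(PASI1 + c)) with c fixed in advance and justified. Untransformed rPASI is an alternative, but it changes the covariate form for every patient. Use the same definition in the Synopsis, M1, the Cmin analysis and the TSAP.

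State that PASI 0 at Week 14 is an observed value and no reason to leave M1 when the response, Week 14 weight, stage and the Week 12-14 PK value are available. Say in Section 7.4.1 whether such a patient counts as PK evaluable.

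Section 11.2 (Amendment 2) records that the blinded re-assessment has been done and that the study remains blinded. PASI 0 cases can therefore be counted now without unblinding, and it can be reported how any such case entered the variance estimate.

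The cost is one covariate definition and no new data. It is, however, a further change to the primary model after the re-assessment, so the blinded variance estimate and the justification of the 4.9% level must be rechecked under the new form. Covariate fit may shift slightly, and the choice of c affects the leverage of cleared patients.

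### Section 7.3.1 gives model M1 arm-specific error variances but the equivalence rule a single residual SD; if the Fieller interval is pooled too, the error at the 80% margin can modestly exceed 5%

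*Protocol*

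**What the plan says.** All of this is in the Protocol.

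- **Level and margins (Section 7.2).** "For the primary endpoint analysis the BE margins 80% - 125% on the ratio scale will be applied". On the level: "A (one-sided) significance level 4.9% was chosen to ensure overall type I error control at 5%, in light of the adapted analysis strategy", with details left to the TSAP.
- **Decision rule (Section 7.3.1).** "The ratios of the means including their two-sided 90.2% CIs will be calculated", using Fieller's theorem. Equivalence needs the interval to lie within 80.00–125.00% and, in addition, |Ȳ_R| / (σ̂·√(1/n_R)) > t with n_T+n_R−5 df. The section says that this pair of conditions amounts to rejecting both null hypotheses. It defines σ̂ thus: it "is the residual standard deviation from the ANCOVA model (M1) below".
- **Error term of M1 (Section 7.3.1).** The model is introduced with "where the random errors are assumed to be independent and normally distributed with zero mean and variance" σ_k², k being test or reference.
- **Mean structure.** Section 7.3.1 lists treatment, log(rPASI), weight, the Week 12–14 PK value and "Stage, where stage represents the two parts of the study prior to and after the blinded sample size reassessment". The Synopsis describes an ANCOVA "on the original scale including effects for" treatment, log(rPASI), weight and the baseline PK value, without stage.
- **Software.** Section 7.3.1 names PROC MIXED with LSMEANS. It neither states nor excludes a group-specific residual variance.

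**The concern.** A model with variances σ_T² and σ_R² has no single residual SD, and its reference distribution does not have df equal to sample size minus parameter count. The σ_k² statement and the σ̂ statement therefore cannot both describe the confirmatory analysis, and a programmer would have to choose between them.

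The choice matters because this is a test on a ratio. For a simple difference, 1:1 allocation largely protects a pooled variance. For T − θR it does not, because the reference variance enters with weight θ²: 0.64 at the 80% margin and 1.5625 at the 125% margin. The 4.9% level leaves only 0.1 percentage point below 5%.

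The Protocol's own rationale makes a larger switching-arm variance conceivable. Section 3.2 reasons that switching might raise ADA formation and lower exposure, and Section 7.3.5 keeps BLQ values in the analysis as ½ LLOQ. Any excess would then fall at the 80% margin, which is the direction the trial is meant to guard.

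**Working it through.** **1. The plan's own figure.** 1 − 2 × 0.049 = 0.902, so the 90.2% interval matches the 4.9% one-sided level.

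**2. Degrees of freedom.** M1 has six mean parameters: intercept, treatment, log(rPASI), weight, stage and baseline PK. A common-variance fit would leave n_T+n_R−6 df, not −5. At 86 per arm (Synopsis), t(0.951) is 1.66394 on 167 df and 1.66400 on 166 df. The slip has no practical effect.

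**3. The displayed condition.** With σ̂ expressed as a CV of the reference mean, the statistic is √86/CV. This is 18.5 at CV 50% and 9.3 at CV 100%, against a critical value of 1.66. It is met easily whichever SD is used, so it does not drive the error rate. The Fieller interval does.

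**4. Which variance the interval uses.** The Protocol does not write it out. A Fieller interval is bounded only if the denominator mean is significant under the same variance estimate and t quantile that build the interval. The section's claim that the two conditions together equal rejecting both nulls is therefore exact only if the interval shares σ̂ and those df. That points to a pooled interval, but it remains an inference.

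**5. Error rate if the interval is pooled.** Let v be the variance ratio, test over reference, with σ_R² = 1 and equal arms. At a true ratio θ, up to the common factor 1/n:

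- variance assumed by pooling: (v+1)/2 × (1+θ²)
- true variance: v + θ²
- one-sided error ≈ P(Z > 1.66394 × √(assumed/true))

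| v | θ | assumed | true | √(assumed/true) | critical value | error |
|---|---|---|---|---|---|---|
| 1.5 | 0.80 | 2.050 | 2.140 | 0.979 | 1.629 | 5.2% |
| 2 | 0.80 | 2.460 | 2.640 | 0.965 | 1.606 | 5.4% |
| 3 | 0.80 | 3.280 | 3.640 | 0.949 | 1.580 | 5.7% |
| 2 | 1.25 | 3.844 | 3.563 | 1.039 | 1.728 | 4.2% |
| 3 | 1.25 | 5.125 | 4.563 | 1.060 | 1.764 | 3.9% |

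The normal approximation runs about 0.1 point low: at v = 1 it gives 4.8%, not 4.9%.

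**6. Simulation check.** Two-sample, 85 per arm (170 PK-evaluable patients, Section 7.4.1), 4 million draws per cell, by SD ratio test/reference:

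| SD ratio | error at 0.80 | error at 1.25 |
|---|---|---|
| 1.00 | 4.9% | 4.9% |
| 1.05 | 5.0% | 4.8% |
| 1.10 | 5.1% | 4.7% |
| 1.25 | 5.3% | 4.5% |
| 1.50 | 5.6% | 4.2% |
| 2.00 | 6.0% | 3.8% |

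Ratios below 1 mirror this: at 0.80 the errors are 4.5% at the 0.80 margin and 5.3% at the 1.25 margin. Arms of 80 (test) and 90 (reference) with SD ratio 1.5 give 6.0% at 0.80.

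**7. After the change.** An ANCOVA simulation (four covariates, full decision rule, 85 per arm, assumed residual CV 40%, SD ratios 0.5 to 2) with arm-specific variances gives 4.8–5.1% at the margin, which is the nominal level within simulation error. With equal variances and CV 40%, power is 94.7% under either method.

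**The case against.** The wording conflict is hard to dispute, but there is a good case against building much on it.

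- **A reader might infer that the Protocol specifies a pooled equivalence test and so fails to control type I error.** The documents do not say this. The formula containing σ̂ is the check on the reference mean, the interval's variance is unstated, and σ_k² in M1 points the other way. This stands as a limit: the error figures depend on the pooled reading.
- **A reader might also infer that any difference in variance pushes the error above 5%.** That is too general. With 1:1 arms the excess is at one margin only. If the two arms have equal CVs, so that SD scales with the mean, both margins are conservative (about 4.5%). With 75 test and 95 reference patients and an SD ratio of 0.5 to 0.9, neither margin exceeds 4.9%. When variability is high enough that both one-sided tests bind together, the excess disappears.
- **No arm-level SD is given.** The variance ratios are assumptions, and higher variability after switching is a hypothesis.
- **The type I error justification is deferred to the TSAP** (Sections 7.2 and 7.4.1), so what the 4.9% allowance covers cannot be judged here. That is fair, but the Protocol itself fixes σ_k², σ̂, the df and the level. A justification in the TSAP needs one defined model to refer to.
- **Stage is clear in the main text.** It appears in the effect list and the M1 equation, and Section 7.4.1 removes it by name for the blinded review. Its absence from the Synopsis is only a clean-up.

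**Conclusion.** The point holds as a specification conflict in the primary analysis with a modest, conditional effect on the error rate. Section 7.3.1 cannot be followed as written, because its model has two error variances and its rule has one.

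If the Fieller interval is pooled, the switching arm is the more variable one and the arms are near balance, the one-sided error at the 80% margin is about 5.2% to 5.7% for variance ratios of 1.5 to 3. The 0.1-point allowance is used up once the SDs differ by roughly 5 to 10%. The 125% margin becomes conservative. These are errors for a single endpoint. Because both endpoints must pass, they bound the trial-level error from above.

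An actual excess cannot be shown from the Protocol. The df count and the missing stage term in the Synopsis are real but numerically immaterial. The change should be made, because it is cheap and removes an ambiguity in the confirmatory test.

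**What to change.** Preferred: make the analysis follow the variance that M1 states.

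1. Fit M1, with stage, in PROC MIXED using group-specific residual variances (REPEATED with GROUP=treatment).
2. Build the Fieller interval from the estimated variances and covariance of the two LSMeans, with Satterthwaite-type df.
3. Write the reference-mean condition as |LSMean_R| / SE(LSMean_R) > t with matching df.
4. Add stage to the Synopsis model.

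If the sponsor intends a common variance instead, replace σ_k² by σ², use n_T+n_R−6 df, state that the Fieller interval uses the same σ̂, and confirm that the 4.9% level still holds 5% under plausible unequal variances. Stage still has to be added to the Synopsis.

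Either route costs a few sentences in Section 7.3.1 and the Synopsis and a few lines of code. It should be settled before unblinding. The preferred route showed no loss of power at equal variances in the case checked (94.7% either way at CV 40%).
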